**STUDY SUMMARY:** 

Full title	Missed opportunities for improving outcomes in Chronic
	Obstructive Pulmonary Disease in underserved populations
Health condition studied	Chronic Obstructive Pulmonary Disease (COPD)
Study type	Mixed methods explanatory sequential study design consisting
	of two phases quantitative followed by qualitative
Participants	
 
Work package 1 (WP1): quantitative modelling of publicly
 

	available data to estimate the magnitude of
	underdiagnosis of COPD in General Practice in England
	Work package 2 (WP2): Cross-sectional prevalence survey
	randomly sampling 4,761 people from two primary care
	networks in deprived areas, offering a breathing
	assessment (est. 30% uptake with a 7% prevalence)
	creating a cohort of 100 patients with COPD.
	Work package 3/4 (WP3/4) Semi-structured interviews
	with health professionals (10-15) and people living with
	COPD (15-25) purposively sampled informed by findings
	Trom WP1-2.
	WORK package 5 (WP5): Co-design workshops will be new
	With representation from key stakenoiders (patients,
	nealth professionals, managers, integrated care boards) to
Study duration / length	60 months (5 years)
Start date	1 December 2024
Fnd date	1 December 2024
Key study milestones	
 
Project set-up: study months -2 to 5 (October 2024 to April)
 

Rey study milestones	2025)
	
 
Quantitative modelling study (WP1): study months 0 to 24
 

	(December 2024- December 2025)
	
 
Cross-sectional prevalence survey (WP2): study months 10
 

	to 50 (September 2025- December 2028)
	• Qualitative studies (WP3/4): study months 22 to 48
	(September 2026-December 2028)
	• Co-design workshops and Stakeholder dissemination event
	(WP5): sudy months 48 to 60 (December 2028 – December
	2029
Funder	NIHR Advanced fellowship NIHR303606
Principle Investigator	
	[name], NIHR Advanced Fellow
	[name], NIHR Advanced Fellow Sheffield Centre for Health and Related Research
	[name], NIHR Advanced Fellow Sheffield Centre for Health and Related Research University of Sheffield, [name]

Protocol Version 0.2, 3rdth February 2025 **KEY WORDS:** 

Chronic Obstructive Pulmonary Disease Non-communicable Chronic Respiratory Diseases Underserved populations Mixed methods Minoritised ethnic groups Co-design Prevalence survey Breathlessness

### LIST OF ABBREVIATIONS:

COPD	Chronic Obstructive Pulmonary Disease
DECRN	Deep End Clinical Research Network
PCN	Primary Care Network
GOLD	Global Initiative for Obstructive Lung Disease
QOF	Quality and outcomes framework
SSC	Study Steering Committee

#### 1 INTRODUCTION

# 1.1. Brief Overview

Chronic Obstructive Pulmonary Disease (COPD) is a preventable and treatable chronic lung disease affecting three million people in the UK and is associated with a substantial healthcare burden. COPD is commoner in deprived communities and associated with risk factors such as smoking, air pollution and poor housing. People living with COPD in the most deprived areas are up to ten times more likely to have poor outcomes compared to those in the least deprived areas, with increased morbidity and mortality.

Some ethnic minority groups are at higher risk of developing COPD as they are more likely to smoke and live in the most income-deprived neighbourhoods. They are also more likely to have COPD unrelated to smoking, and those that are first generation immigrants are likely to have alternative risk factors. Despite this, the proportion of ethnic minorities diagnosed with COPD appear lower than expected with little research conducted in this area.

The aims of this work are:

To determine the burden of disease caused by COPD in underserved populations and why it may be under-estimated.

To explore barriers and enablers of primary care interventions (vaccination, pulmonary rehabilitation, and treatment of tobacco dependency) for people diagnosed with COPD in under-served populations.

The associated research questions are:

To what extent is COPD under-detected in under-served (socioeconomically deprived and/or ethnic minority) populations, and what are the main reasons for this?

Why do primary care interventions (vaccination, pulmonary rehabilitation, and treatment of tobacco dependency) for supporting people with COPD fail to reach underserved populations?

#### Summary of methods 1.2

This is a mixed methods, explanatory sequential design consisting of two distinct phases: quantitative followed by qualitative. There are five work packages (WP); WP1-2 Quantitative phase, WP3-4 Qualitative phase and WP5 Interpretation of results and intervention codevelopment.

**WP1**: This will provide an estimation of the number of patients with undiagnosed COPD in underserved populations nationally using publicly available data. This will be compared with prospectively collected data from WP2.

**WP2:** The prevalence of COPD in underserved primary care populations will be established in people from underserved communities registered in two primary care networks.

WP3: An understanding of barriers and facilitators to recognising COPD in underserved populations will be generated through a semi-structured interviews, informed by WP1-2.

WP4: An understanding of how COPD and key primary care interventions (vaccination, pulmonary rehabilitation, and treatment of tobacco dependency) are perceived by underserved populations will be generated through the semi-structured interviews, leveraging the cohort established in WP2.

WP5: Findings from WP1-4 will be integrated and interventions co-developed to improve recognition and management of people with COPD in underserved populations.

#### Main benefits of research 1.3

Recognising underserved people with COPD and intervening early could reduce the burden of this condition on both patients and the health system. Primary care-based interventions, improve health, reduce exacerbations and are the most cost-effective for COPD. This study provides valuable information from voices seldom heard allowing co-development of fit for purpose interventions. Findings will be disseminated through publication, social media, community groups and existing stakeholder networks.

#### Study flow chart 1.4

See Figure 1

### 2 BACKGROUND AND RATIONALE

#### 2.1 What is the problem being addressed?

Chronic obstructive pulmonary disease (COPD) is a preventable and treatable chronic lung disease affecting three million people in the UK and is associated with a substantial healthcare burden. It is the fourth leading cause of death globally and accounts for 10% of all premature deaths in England annually. Data from four epidemiological studies in 27 countries demonstrated that COPD was undiagnosed in >50% of people, and 79.6% of COPD cases in London were previously undiagnosed. Patients with undiagnosed COPD are often first encountered in primary care, but opportunities for diagnosis are commonly missed. COPD is commoner in deprived communities, where risk factors for COPD such as smoking, air pollution, occupation, and poor housing are more common. People living with COPD in the most socioeconomically deprived areas are up to ten times as likely to have increased morbidity and mortality compared to those in the least deprived areas. Some ethnic minority groups are likely to be at higher risk of developing COPD as they are more likely to smoke and live in the most income-deprived neighbourhoods (e.g. >25% Pakistani men smoke and 30.7% live in deprived neighbourhoods). Current approaches to COPD diagnosis are opportunistic and reliant on a history of tobacco dependency. Emerging data has identified COPD unrelated to smoking ('non-smoking COPD') as more likely in patients from ethnic minority backgrounds, who have other risk factors such as increased infections in childhood and exposure to indoor air pollution from cooking stoves. The latter may increase the risk of COPD in non-smoking women in particular.

A recent multivariable analysis conducted using publicly available data from all general practices in Sheffield showed that the greater the percentage of ethnic minorities in a practice, the lower the percentage of patients diagnosed with COPD (adjusting for age, smoking and decile of index of multiple deprivations). The same pattern is observed within South Yorkshire regional and general practice data from England as a whole. These data suggest that current strategies used for recognising COPD are disproportionately missing cases in ethnic minority populations at high risk of COPD. Further work is required to confirm this at the level of individual patients.

This study will explore diagnosis of COPD in populations from deprived and/or ethnic minority backgrounds, estimating the extent of underdiagnosis in these populations. Furthermore, perceptions of COPD and primary care interventions for COPD (vaccination, pulmonary rehabilitation, and treatment of tobacco dependency) will be explored, facilitating co-development of strategies to improve patient uptake of these interventions and improve health outcomes.

#### Why this research is important? 2.2

The extent and impact of underdiagnosis of COPD in socioeconomically deprived and/or ethnic minority populations is unknown. However, people with undiagnosed moderate-to-severe COPD have higher hospitalisation rates, increased symptoms, and poorer health-related quality of life than people without COPD. The impact of undiagnosed COPD is likely to be greatest in the most deprived areas, where the burden of disease is highest.

A first acute presentation to hospital with COPD represents a missed opportunity for exacerbation prevention through prior early diagnosis. One-fifth of patients for whom hospitalisation is their first COPD presentation die within one year of discharge. COPD is responsible for one-in-eight emergency hospital admissions in the UK and COPD admission rates are associated with deprivation. One of the five clinical focus areas in NHS England's Core20PLUS5 (adults) approach to reducing healthcare inequalities is chronic respiratory disease, specifically targeting COPD vaccination uptake and exacerbation rate reduction. Underdiagnosis and limited uptake of evidence-based interventions for COPD are long-standing problems, leading to significant excess morbidity and mortality in the most deprived areas. Early diagnosis and treatment (e.g. vaccination, pulmonary rehabilitation, treatment of tobacco dependency) are important in reducing symptom burden, improved health related quality of life, reducing mortality, and reducing the cost impact of COPD. Improving timely diagnosis and engagement with COPD care in the most deprived areas will reduce demands on the health system in an already overburdened NHS.

#### 2.3 How does the existing literature support this study

The Burden of Obstructive Lung Disease (BOLD) study has demonstrated that there is a high prevalence of undiagnosed COPD in multiple settings globally. The overall prevalence was 10.1% using data across 12 sites. In the UK, around 2% of the population and 4.5% of people aged >40 years live with diagnosed COPD. This would suggest that 5.6% of people with COPD remain undiagnosed, but the prevalence in underserved populations remains unknown.

The underdiagnosis of COPD is an issue in general practices in deprived communities, within which there are often significant populations of people from ethnic minority backgrounds. Irrespective of age, smoking, and socioeconomic status, lower percentages of COPD diagnosis are seen in general practices in England with higher percentages of ethnic minority populations. Current strategies for identifying people with COPD in the UK almost exclusively require patients to be smokers. This approach is likely to disproportionately miss cases in populations with greater proportions of non-smoking COPD such as ethnic minority groups. The 2023 Global Initiative for Chronic Obstructive Lung Disease (GOLD guidance) notes the heterogeneity of processes that contribute to COPD such as premature birth,

childhood infections, tuberculosis, and household or ambient air pollution. It highlights that COPD is no longer considered a single disease caused by tobacco smoking, but multiple subtypes defined by functional or pathobiological mechanisms.

Prior research on how to address underdiagnosis has focused predominantly on case finding strategies targeted at active smokers in primary care in predominantly white British populations. The NIHR BLISS programme grant conducted a trial among smokers (85% white British) to identify new cases of COPD and used routinely collected primary care data to develop the TargetCOPD score to identify patients at high risk of having COPD. The validity of using this score in people with COPD from ethnic minority backgrounds who have never smoked is unknown.

Primary Care interventions for patients with COPD: COPD forms part of the quality outcomes framework (QOF) in general practice and therefore once diagnosed, patients are added to a register to target on-going disease specific care. Despite this, uptake of evidence-based primary care interventions for COPD was low in the most socioeconomically deprived areas in Sheffield. Less than 50% of patients with COPD agreed to pulmonary rehabilitation referral or to pneumococcal or influenza vaccinations. This is in keeping with previous findings demonstrating that socioeconomic status has a consistent impact on COPD morbidity and mortality, suggesting that lack of engagement with evidence-based primary care interventions for COPD could be a contributory factor to poor outcomes for those living in deprived areas.

Vaccinations, pulmonary rehabilitation, and treatment of tobacco dependency are the most cost-effective interventions as indicated by the London Respiratory Network 2013 value pyramid. Vaccines are an effective preventative measure for reducing respiratory infections and hence exacerbation frequency in patients with COPD. In Deep End general practices in Sheffield, only a median of 60.8% (IQR 58.6,62.8) of people with COPD received seasonal influenza vaccination and only a median of 24.4% (IQR19.6,36.0) had ever received a pneumococcal vaccination. Whether this reflects the nationwide poor uptake of influenza vaccination in individuals <65 years in clinical risk groups or added issues of delivery to underserved populations requires further investigation.

Pulmonary Rehabilitation (PR) is a highly effective education and graded exercise intervention for the management of COPD, but there is a need to understand why uptake of PR in primary care has been consistently poor. A median of 47% patients with COPD in Deep End general practices in Sheffield declined referral for PR. Previous studies have identified multiple barriers at the interfaces between PR services, primary care, and patients with COPD. Issues around language barriers and transport were highlighted as specific to the South Asian community. This study will involve underserved communities to increase understand of, and co-design healthcare solutions at the primary care level for patients diagnosed with COPD.

Finally, there is high-quality evidence that COPD patients that smoke are over twice as likely to quit when they receive behavioural support and medication compared to those that receive behavioural support alone. A systematic review of the impact of specialist and primary care tobacco dependency services on socio- economic inequalities in cessation highlighted the paucity of data available. In Scotland, where adequate data were available, lower quit rates were seen in patients from low socioeconomic groups. An understanding of perceptions of patients with COPD from underserved communities around treatment of tobacco dependency and how it is delivered is needed to inform the delivery of future care.

A recent scoping review of co-creation practices for COPD identified only four studies conducted in the UK, all of which involved either supported self-management strategies or utilisation of mobile applications. No co-creation studies have explored improving implementation of multiple primary care-based interventions for COPD in underserved populations. This project will identify and add patients to COPD registers, in line with NICE guidance, and will target implementation of healthcare strategies to understand recognition and management of people with COPD from underserved communities.

### AIMS AND OBJECTIVES 3

# 3.1 Aims

To determine the burden of disease caused by COPD in underserved populations and why it may be under-estimated.

To explore barriers and enablers of primary care interventions (vaccination, pulmonary rehabilitation, and treatment of tobacco dependency) for people diagnosed with COPD in underserved populations.

#### 3.2 **Objectives**

Estimate the number of people with undiagnosed COPD in underserved populations in England (WP1)

Determine the actual prevalence of undiagnosed COPD in an underserved primary care populations (WP2).

Understand barriers and facilitators to recognising COPD in underserved populations (WP3).

Understand how COPD and its primary care interventions (smoking cessation, pulmonary rehabilitation, and vaccination) are perceived in underserved populations (WP4).

Co-develop interventions to improve uptake of primary care interventions (smoking cessation, pulmonary rehabilitation, and vaccination) for COPD in underserved populations (WP5)

### STUDY DESIGN/ METHODS 4

#### Overall design and conceptual framework 4.1

This is a mixed methods explanatory sequential study design consisting of two phases: quantitative followed by qualitative leading to co-design of an intervention. The quantitative data on COPD in underserved populations will be sought first through modelling of publicly available General Practice data (WP-1) and a cross-sectional prevalence survey (WP-2) conducted in North Sheffield Primary Care Networks. The qualitative data will be collected second informed by the findings from WP-1 & 2. This will explore and explain the findings from the quantitative results, through semistructured interview studies (WP-3 & 4) of health care professionals, patients and carers in North Sheffield Primary Care Networks. The two phases will be integrated at analysis. The rationale for this approach is that the quantitative data and their subsequent analysis provide a general understanding of the research problem. The qualitative data and their analysis refine and explain those statistical results by exploring participants' views in more depth. (Cresswell et al. 2003) Finally these data will look to inform co-design of an intervention (WP-5) to address the findings from WP-1-4

#### 4.3 Quantitative modelling study (WP1)

In WP-1 national routinely collected public data sets; Fingertips, NHS digital and the Office National Statistics will be used to model the expected prevalence of COPD in General Practices in England. Publicly available general practice variables known to be associated with COPD such as tobacco dependency, age and deprivation will be used to create model estimates of the expected prevalence of COPD in general practice.

# Data Analysis:

Regression analysis will be used to predict expected COPD prevalence in each general practice in England, based on the prevalence of risk factors (e.g. tobacco dependency, poor housing, age and deprivation) and their magnitude of association with COPD from published literature. These expected COPD rates will be compared with NHS digital actual prevalence data in general practices from COPD QOF registers. This will allow estimated to be made of the shortfall in COPD diagnosis nationally at a general practice level. Factors that may be associated with underdiagnosis of COPD such as the percentage of patients from ethnic minority backgrounds will be explored. The model estimates of COPD prevalence will also be compared with the 2010 Health Survey for England Data on respiratory and lung health which included a subset of people who underwent spirometry to diagnose COPD.

As this will utilise routinely collected data already in the public domain no formal ethical approval is required to conduct this work.

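### WP1's link between ethnicity and the COPD shortfall mixes differences in true risk with differences in detection, in either direction

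*Protocol*

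**What the plan says.** Protocol section 4.3 introduces the predictors: "Publicly available general practice variables known to be associated with COPD such as tobacco dependency, age and deprivation will be used". Its Data Analysis paragraph gives a similar list; the prediction is "based on the prevalence of risk factors (e.g. tobacco dependency, poor housing, age and deprivation) and their magnitude of association with COPD from published literature". Both lists are given as examples. Ethnicity is in neither.

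The comparison follows: "These expected COPD rates will be compared with NHS digital actual prevalence data in general practices from COPD QOF registers". The resulting gap is named a "shortfall in COPD diagnosis nationally at a general practice level". Ethnicity then enters, as a correlate of that gap: "Factors that may be associated with underdiagnosis of COPD such as the percentage of patients from ethnic minority backgrounds will be explored".

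The background takes a position on true risk. Section 2.1 links COPD unrelated to smoking in ethnic minority patients to childhood infections and to indoor air pollution from cooking stoves. Neither exposure is a named predictor in section 4.3. Section 2.3 refers to "populations with greater proportions of non-smoking COPD such as ethnic minority groups". On earlier practice-level findings, section 2.1 adds a caveat: "Further work is required to confirm this at the level of individual patients".

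Two outside checks are planned: the spirometry subset of the 2010 Health Survey for England (section 4.3) and the WP2 survey (sections 1.2 and 4.4). Neither is stated to be made by ethnic group.

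**The concern.** The register records true prevalence multiplied by the share of cases detected. If the expectation takes no account of ethnicity, practices with many ethnic minority patients can show a larger or smaller gap for two reasons: their true risk differs at the same age, smoking and deprivation, or their cases are found less or more often. Practice-level data alone cannot tell these apart, yet the text treats the gap as underdiagnosis.

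This touches the first research question, how far COPD is under-detected in deprived and ethnic minority populations (section 1.1). WP1 findings also feed the sampling and interview content of WP3 and WP4. Moreover, section 2.1 already reports lower register COPD in practices with more ethnic minority patients after adjustment for age, smoking and deprivation, with the same pattern in England-wide practice data. WP1's named factors nearly repeat that adjustment, so a gradient in the gap is largely foreseeable and would not by itself settle risk against detection.

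**Working it through.** WP1 states no sample size, effect size or precision to reproduce. The check is an identity with illustrative inputs.

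**Notation.** Expected prevalence E = p, ignoring ethnicity and calibrated to the reference group. True prevalence T = p × [(1 − m) + m × RR], where m is the minority share and RR the risk ratio given the modelled factors. Register R = d × T, where d is the share detected, set equal in all groups. Apparent undiagnosed share = (E − R)/E. True undiagnosed share = 1 − d.

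**Inputs from the protocol.** p = 7% (section 4.4, Sample size; a WP2 figure for people over 35, used only as a base). d = 4.5/10.1 = 0.446 (section 2.3; the two percentages come from different populations, so this is illustrative). **Assumed:** m and RR.

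**One practice with m = 60%.**
- RR 0.7: 7% × (0.4 + 0.6 × 0.7) = 5.74%. The model expects 1.26 points too much. With nobody missed, that appears as a shortfall of 18% of expected.
- RR 1.3: 7% × (0.4 + 0.6 × 1.3) = 8.26%. The model expects 1.26 points too little, and that much real underdiagnosis can be hidden.

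The 18% does not depend on the 7% base, since 0.6 × 0.3 = 0.18.

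**Gradient between practices with m = 5% and m = 60%, d = 0.446.** The true undiagnosed share is 55.4% in both.

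| RR | Apparent, m = 5% | Apparent, m = 60% | Spurious difference (points) |
|---|---|---|---|
| 0.5 | 56.6% | 68.8% | +12.3 |
| 0.75 | 56.0% | 62.1% | +6.1 |
| 1.0 | 55.4% | 55.4% | 0 |
| 1.25 | 54.9% | 48.8% | −6.1 |
| 1.5 | 54.3% | 42.1% | −12.3 |

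At RR 1.5 and m = 60% the apparent shortfall is 7 − 0.446 × 9.1 = 2.95 points, against a true one of 9.1 − 0.446 × 9.1 = 5.05 points.

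**National total.** At an assumed 20% minority share, RR 0.7 or 1.3 moves the correct expectation by 0.2 × 0.3 = 6%.

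**Can WP2 decide?** The planned numbers reproduce: 4,761 × 0.30 = 1,428, and 1,428 × 0.07 = 100. Assuming an equal split, each primary care network (PCN) has 714 people. Power of a two-sided 5% comparison of the PCNs is 28% for 7% against 5.25% and 23% for 7% against 8.75%. It is 84% for 7% against 3.5% and 65% for 7% against 10.5%. In the first two cases the 95% half-width of the difference is 2.5 and 2.8 points, against a difference of 1.75.

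**The case against.** Several points on the other side stand.

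- **Open lists.** A reader might infer that ethnicity is excluded from the model and equal risk is assumed by design. The text does not go that far: both lists are examples, and the final covariates may be set in an analysis plan not shown here. What the text does fix is the role it gives ethnicity, as a correlate of underdiagnosis, and the name it gives the gap.
- **Direction.** A reader might infer that any true ethnic difference in risk will be reported as missed diagnosis. That holds only where risk, given the modelled factors, is lower in minority groups. The protocol's premise is higher risk, and then the model understates the shortfall.
- **Evidence for a residual difference.** Part of the higher risk described in section 2.1 runs through smoking and deprivation, which are named predictors. The section 2.3 remark on non-smoking COPD describes case mix, not total risk. Only childhood infections and indoor air pollution clearly point to risk outside the named factors.
- **Planned safeguards.** The ethnicity link is only to be explored, section 2.1 asks for individual-level confirmation, WP2 records ethnicity for each participant (section 11.1.3), and two comparisons with spirometry data are planned. These could expose the problem. But no comparison by ethnic group is stated, and WP2 is weak for moderate differences.

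**Conclusion.** The point holds as a limit on what WP1 can conclude about ethnicity. As described, the gradient of the gap over percentage ethnic minority confounds true risk with detection, and the bias can go either way. At a 60% minority share, risk ratios of 0.7 and 1.3 misplace the expectation by 18%. Ratios of 0.5 to 1.5 create differences of up to 12.3 points in apparent undiagnosed share where detection is identical. The risk ratios, the minority shares and equal detection are assumptions.

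Two stronger conclusions are not supported. A reader might infer that the national shortfall is mainly a product of an equal-risk assumption. At the assumed 20% share the expectation moves by about 6%, while section 2.1 cites more than half of COPD as undiagnosed; the effect falls mainly on the gradient and on practices with a high minority share. A reader might also infer that WP2 will show which risk ratio is right. It can inform this but not settle it: section 4.4 limits spirometry to symptomatic participants, so WP2 does not measure all airflow obstruction by ethnic group, and power between two PCNs is 23% to 28% for differences of 1.75 points.

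**What to change.** In section 4.3, Data Analysis:

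1. Run the expected-prevalence model with ethnicity-specific risk ratios of 1.0, below 1.0 and above 1.0, taken from published estimates where available. Estimates based on spirometry are preferable, because those based on recorded diagnoses carry the same mixture of risk and detection.
2. Report the ethnicity gradient and the shortfall as a range across these runs.
3. Call the WP1 output a 'shortfall against model' rather than underdiagnosis, and state that its ethnicity gradient may reflect risk, detection or both.
4. Compare the model with the Health Survey and WP2 data by ethnic group where numbers allow, and say that WP2 informs the choice of scenario but cannot settle it, for the reasons of symptomatic-only spirometry and low power.

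The cost is two further runs of the same model and some wording; no new data collection is needed. The downside is that WP1's ethnicity result becomes a range.
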